6.2. Secondary Outcomes

Secondary outcomes will be the changes in the OCD-VAS and Y-BOCCS total score from baseline to 14 days post infusion.

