 - o Medical assessment: Vital Signs and Pregnancy Test (urine) for female participants

Note: If a patient's score on the Global Improvement section of the CGI is a 6 ("much worse") or 7 ("very much worse") compared to baseline at the day 3 or 4 study visit, the clinician will take the

patient off the protocol and initiate the 3-month open clinical treatment offered to all patients at the end of the study.

- *Day 7 post-infusion:* Participants complete the following assessments at the CDU or over the phone (if participants live far away):
 - IE ratings: Children's Yale-Brown Obsessive Compulsive Scale (CYBOCS), Children's Depression Rating Scale-Revised (CDRS-R), Clinical Global Impressions Scale (CGI).
 - MD ratings: Columbia-Suicide Severity Rating Scale (C-SSRS), Young Mania Rating Scale (YMRS), Clinician Administered Dissociative States Scale (CADSS), Brief Psychiatric Rating Scale (BPRS), Clinical Global Impressions Scale (CGI).
 - Self-report forms: OCD Visual Analogue Scale (OCD-VAS), Yale-Brown Obsessive Compulsive Challenge Scale (YBOCCS), Child Obsessive-Compulsive Impact Scale-Revised (COIS-R).
 - Medical assessment: Vital Signs and Pregnancy Test (urine) for female participants

Note: If a patient's score on the Global Improvement section of the CGI is a 6 ("much worse") or 7 ("very much worse") compared to baseline at the day 7 study visit, the clinician will take the patient off the protocol and initiate the 3-month open clinical treatment offered to all patients at the end of the study.

- *Day 8-13 post infusion:* OCD-VAS and YBOCCS are administered daily during optional phone calls.
- *Day 14 post-infusion:* Participants come to the CDU to complete the following assessments:
 - IE ratings: Children's Yale-Brown Obsessive Compulsive Scale (CYBOCS), Children's Depression Rating Scale-Revised (CDRS-R), Clinical Global Impressions Scale (CGI).
 - MD ratings: Columbia-Suicide Severity Rating Scale (C-SSRS), Young Mania Rating Scale (YMRS), Clinician Administered Dissociative States Scale (CADSS), Brief Psychiatric Rating Scale (BPRS), Clinical Global Impressions Scale (CGI).
 - Self-report forms: OCD Visual Analogue Scale (OCD-VAS), Yale-Brown Obsessive Compulsive Challenge Scale (YBOCCS), Child Obsessive-Compulsive Impact Scale-Revised (COIS-R).
 - o Medical assessments: Safety labs, vital signs, pregnancy test (urine) for female participants.

Follow-up Treatment

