Clinician Administered Dissociative States Scale (CADSS): This is a clinician rated instrument for rating degree of dissociation. A severity scale will be added: mild, moderate, severe for those items endorsed on interview. It will be administered by the study MD at baseline, 20 minutes from the start of the infusion, immediately post-infusion, 60 and 120 minutes post-infusion, day 3 or 4, day 7, and day 14.

Brief Psychiatric Rating Scale (BPRS): The BPRS is an 18-item observer-scale designed to assess patients with major psychiatric disorders, particularly schizophrenia. The BPRS measures positive symptoms, general psychopathology and affective symptoms. Some items (e.g. mannerisms and posturing) can be rated simply on observation of the patient; other items (e.g. anxiety) involve an element of self-report by the patient. The BPRS is administered by a trained clinician via a semi-structured interview at baseline, 120 minutes post-infusion, day 3 or 4, day 7, and day 14.

OCD Visual Analogue Scale (OCD-VAS): A one-item scale to assess OCD symptoms over a rapid time frame. Patients will be asked to report their rating on this scale prior to, during and after the infusion as per the study flowchart.

Child Obsessive-Compulsive Impact Scale-Revised (COIS-R): This 27-item self-report questionnaire measures OCD-specific functional impairment. The COIS-R-C is a 3-factor structure youthreport form. The COIS-R-P is a 4-factor structure parent-report measure (completed by the parent/caretaker for those <18 and those 18-22 with permission). Participants and their parents will be asked to complete the COIS-R at baseline, day 7, and day 14.

Yale-Brown Obsessive Compulsive Challenge Scale (YBOCCS): A brief self-report scale to assess rapid changes in OCD symptoms. Patients will be asked to report their rating on this scale prior to, during and after the infusion as per the study flowchart.

Family History Screen (FHS): This screens for the presence of 15 psychiatric disorders among the participant's biological relatives. It is administered to a family informant (for those ages 8-17) or to the subject (ages 18-22), who reports on himself/herself and on other biological relatives. It will be administered by the MD at screening.

Social Communication Questionnaire (SCQ): This is a 40 item yes-or-no parent questionnaire to screen for autism spectrum disorders.

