3 PROCEDURES

We will recruit 5 adolescents and young adults (post-pubertal, ages 14-20) with OCD using similar criteria as in our prior ketamine study (Rodriguez et al. 2013) with the modification that participants have attempted at least one trial of a standard treatment (i.e., SRI and/or CBT). They will be free of medication and have at least moderate OCD severity (rating on Children's Yale-Brown Obsessive-Compulsive Scale [CY-BOCS] of at least 16) and near constant obsessions. After baseline assessment and evaluation, patients will receive a single infusion of intravenous ketamine 0.5 mg/kg. Obsessional severity will be evaluated at baseline, during the ketamine infusion and during post-infusion observation using the OCD-Visual Analogue Scale; OCD and depressive severity will be evaluated using the CY-BOCS (child version) and Children's Depression Rating Scale Revised at weekly intervals for 2 weeks after infusion.

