5 OUTCOMES

- 6.1. Primary Outcomes
- i. Total number of screened participants
- ii. Total number completing
- 6.2. Secondary Outcomes
- i. CY-BOCS score at baseline, 1 week post-infusion, and 2 weeks post infusion
- ii. Children's Depression Rating Scale Revised at baseline, 1 week post-infusion, and 2 weeks post
- 6.3 Adverse Outcomes
- i. Adverse events will be assessed throughout the study period
- ii. Suicidality will be obtained with the Columbia-Suicide Severity Rating Scale (C-SSRS).

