6 OUTCOMES

6.1. Primary Outcomes

Primary outcomes will be the changes in the CY-BOCS total score and CGI-S rating from baseline to 14 days post infusion.

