8.2. Statistical Tests

In the initial SAP, we proposed a mixed-effects regression to analyze the potential efficacy of the ketamine infusion. After study completion and careful consideration of the data collected, we decided to change the SAP to compare the mean differences of the primary and secondary outcomes between the baseline assessment and 14 days post infusion using paired sample t-tests.

The normal distribution of the differences between the paired values will be tested using the Shapiro-Wilk test and outliers will be reviewed using box plot diagrams. Estimated t-values, 95% confidence intervals, and p-values will be presented for each outcome variable.

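### The revised SAP replaced the secondary outcomes after the data had been considered, gives no reason, and attaches p-values to the new ones without calling them post hoc

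*SAP*

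**What the plan says.** The SAP file holds an initial and a revised version.

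**Initial SAP.** Section 5 makes the numbers screened and completing primary. Its two secondary outcomes are "CY-BOCS score at baseline, 1 week post-infusion, and 2 weeks post infusion" and "Children's Depression Rating Scale Revised at baseline, 1 week post-infusion, and 2 weeks post". Section 8.2 adds the proportions of responders (CY-BOCS fall of at least 35%) and remitters (CY-BOCS of 12 or less) at one and two weeks. OCD-VAS appears in section 3: "Obsessional severity will be evaluated at baseline, during the ketamine infusion and during post-infusion observation using the OCD-Visual Analogue Scale". Section 8.2 then places the baseline to post-infusion difference in obsessional severity in the mixed model. Y-BOCCS appears nowhere.

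**Revised SAP.** Section 6.1 reads: "Primary outcomes will be the changes in the CY-BOCS total score and CGI-S rating from baseline to 14 days post infusion". Section 6.2 reads: "Secondary outcomes will be the changes in the OCD-VAS and Y-BOCCS total score from baseline to 14 days post infusion". Section 8.2 says the mixed model was replaced by paired t-tests once the study was complete and its data had been considered. It continues: "Estimated t-values, 95% confidence intervals, and p-values will be presented for each outcome variable".

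**Protocol.** At day 14 the independent evaluator rates CYBOCS and CDRS-R, and participants complete OCD-VAS, YBOCCS and COIS-R.

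**The concern.** A secondary outcome normally carries some weight because it was named before the results were known. Here the set was renamed afterwards, but the revised section 6.2 presents it as an ordinary secondary list. A reader of the results would take the OCD-VAS and Y-BOCCS p-values as planned secondary findings. The same reader would not learn that a depression scale and two CY-BOCS proportions had been planned and were no longer outcomes.

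The new time point also needs explaining. The protocol's Assessment Instruments section describes both scales as tools for rapid change, and its primary hypothesis concerns the period straight after the infusion. A day-14 test of these scales may be reasonable, but the SAP does not say why it was chosen.

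The stake is practical. The trial is single-arm and small, and its aims section makes promising data the route to a grant application for a full randomized trial. A nominally significant change on a newly promoted self-report scale could be cited as a planned efficacy signal even if CY-BOCS did not move.

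**Working it through.** **Step 1. Compare the lists.**

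| Measure | Initial SAP | Revised SAP | Protocol, day 14 |
|---|---|---|---|
| CY-BOCS | Secondary | Primary | Collected |
| CDRS-R | Secondary | In no outcome list, and gone from section 3 | Collected |
| CY-BOCS responders and remitters | Computed at 1 and 2 weeks (8.2) | Absent | Derivable from CY-BOCS |
| OCD-VAS | Around-infusion measure (3), feeding the model (8.2); not a listed outcome | Secondary, day 14 | Collected |
| Y-BOCCS | Absent | Secondary, day 14 | Collected |
| COIS-R | In no outcome list | In no outcome list | Collected |

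Two planned items leave (CDRS-R; the responder and remitter proportions). Two enter (Y-BOCCS; OCD-VAS at day 14). Data for everything that left are still scheduled, so the protocol's schedule does not explain the removals.

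**Step 2. Look for the reason.** The explanation in revised section 8.2 concerns the statistical test. It refers to the primary and secondary outcomes as if they were fixed and does not say that they changed. Sections 6.1 and 6.2 give no rationale, and no section labels the new outcomes exploratory or post hoc.

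**Step 3. Size of the multiplicity.** The documents state no alpha, sidedness or family-wise error rate, so there is no figure to reproduce.

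Inputs:
- Tests: 2 (revised 6.2).
- Method: paired t-test (revised 8.2).
- Per-test level: two-sided 0.05, assumed.
- n: 5 (SAP section 3), 10 (protocol), and 4 (completers in the protocol's status report).
- Correlation between the changes: unknown, taken as 0 to 0.8.

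If the tests are independent, P(at least one false positive) = 1 − (1 − 0.05)² = 1 − 0.9025 = 0.0975.

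Simulation with correlated normal changes, true change zero, 200,000 replicates per setting:

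| n | correlation 0 | 0.5 | 0.8 |
|---|---|---|---|
| 4 | 0.0975 | 0.0940 | 0.0853 |
| 5 | 0.0984 | 0.0925 | 0.0830 |
| 10 | 0.0979 | 0.0929 | 0.0799 |

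The range is 0.08 to 0.10, or about 1.6 to 2.0 times the single-test level (0.0799/0.05 = 1.6; 0.0984/0.05 = 1.97). Sample size hardly matters. These figures treat the two outcomes as fixed in advance. Any further inflation from choosing them late cannot be quantified from the documents.

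**The case against.** The strongest defence has four parts.

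- **It is a pilot.** The SAP speaks of potential efficacy, states no alpha, and says the tests describe changes. The initial SAP also promised unadjusted p-values, for each outcome and time point. This stands: lack of adjustment is neither new nor serious here, and formal alpha control is not needed.
- **OCD-VAS was not new.** It was the initial SAP's measure of obsessional severity, and that change entered the model. This stands too. What is new is its status as a secondary outcome and the day-14 time point.
- **The choice may have had nothing to do with results.** The protocol's 3-month follow-up battery is CYBOCS, CGI, OCD-VAS and YBOCCS, the same four instruments as in the revised outcome lists. This is a plausible neutral explanation, although the SAP does not offer it.
- **The sponsor disclosed the revision.** That is true of the test, and it is to the sponsor's credit. The disclosure does not extend to the outcomes.

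A reader might also go too far the other way, in three ways.

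- **The scales were picked because they looked favourable.** The documents do not show this. One can calculate about 0.20 for at least one nominally significant result among five day-14 candidates (n = 5, correlation 0.5), but applying it here assumes selection by result.
- **Leaving out COIS-R shows selection.** The protocol does schedule it ("Participants and their parents will be asked to complete the COIS-R at baseline, day 7, and day 14"), but it was an outcome in neither SAP, so nothing changed after the data were considered. YMRS, CADSS and BPRS are likewise among the protocol's efficacy assessments and are outcomes in neither version.
- **The 95% intervals promise a 5% family-wise rate.** They imply coverage for each comparison only.

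**Conclusion.** The concern holds, in a limited form. The secondary set was redefined after the data had been considered: CDRS-R and the responder and remitter proportions went out, and Y-BOCCS and day-14 OCD-VAS came in. No reason is given for the outcome changes, and the new p-values carry no post hoc label. Followed as written, the SAP would present post hoc outcomes as planned ones.

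The fault is mainly one of labelling and completeness. The multiplicity is modest: 0.08 to 0.10 for two tests, assuming two-sided 0.05 per test, normal changes, no true effect and correlation between 0 and 0.8. Selection by result is neither shown nor needed for the point. The strongest evidence is the removal of CDRS-R, a listed secondary outcome that is still collected at day 14. The absence of COIS-R adds nothing to it.

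**What to change.** 1. In revised 6.2, say that the day-14 changes in OCD-VAS and Y-BOCCS are post hoc exploratory outcomes that were not secondary outcomes in the initial SAP, and give the reason for choosing them.
2. In revised 8.2, state that no efficacy conclusion will rest on their p-values alone. The p-values may stay if they are labelled.
3. Restore the day-14 CDRS-R change and the CY-BOCS responder and remitter proportions, identified as originally planned results and reported alongside. State the thresholds used: the initial SAP has a fall of at least 35% and a score of 12 or less, while the protocol's Assessment Instruments section has at least 30% and 10 or less.
4. Optionally, report COIS-R descriptively.

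The cost is a few sentences and a few table rows from data already scheduled. The downside for the sponsor is that the two self-report scales can no longer be cited as planned, significant secondary results.

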6.3 Adverse Outcomes

Adverse events will be assessed throughout the study period; suicidality will be obtained with the Columbia-Suicide Severity Rating Scale (C-SSRS).

7 STATISTICAL ANALYSIS

Data will be analyzed using IBM SPSS. We will report descriptive statistics and results from paired sample-tests to describe changes in primary and secondary outcomes from baseline to 14 days post infusion. The following subsections describe the statistical procedures.

8.1. Descriptive Statistics

All primary and secondary outcomes are continuous variables and descriptive statistics will be reported by mean and standard deviation.

8.2. Statistical Tests

In the initial SAP, we proposed a mixed-effects regression to analyze the potential efficacy of the ketamine infusion. After study completion and careful consideration of the data collected, we decided to change the SAP to compare the mean differences of the primary and secondary outcomes between the baseline assessment and 14 days post infusion using paired sample t-tests.

The normal distribution of the differences between the paired values will be tested using the Shapiro-Wilk test and outliers will be reviewed using box plot diagrams. Estimated t-values, 95% confidence intervals, and p-values will be presented for each outcome variable.

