5 ANALYSIS SET

This pilot study is a non-controlled clinical trial consisting of one group of participants. Participants will be adolescents and young adults with OCD who have failed at least one trial of standard treatment. All participants will receive an intravenous ketamine infusion.

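### The revised SAP ranks day-14 paired t-tests, adopted after the data were considered, as primary without an exploratory label, and leaves the retained feasibility aim with no recruitment or completion outcome

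*SAP*

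**What the plan says.** The SAP document holds an initial and a revised version.

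**Initial SAP.** The primary outcomes (section 5, item 6.1) are two counts, "Total number of screened participants" and the number completing. Section 8.1 reports them as totals and percentages to address acceptability and feasibility. CY-BOCS and CDRS-R at weeks 1 and 2 are secondary. Section 8.2 plans mixed-effects regression over time, plus responder and remitter proportions at both weeks.

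**Revised SAP.** Section 6.1: "Primary outcomes will be the changes in the CY-BOCS total score and CGI-S rating from baseline to 14 days post infusion". Section 6.2: "Secondary outcomes will be the changes in the OCD-VAS and Y-BOCCS total score from baseline to 14 days post infusion". Section 8.1: "All primary and secondary outcomes are continuous variables and descriptive statistics will be reported by mean and standard deviation". Section 8.2 names the mixed-effects regression as the former method and dates its replacement: "After study completion and careful consideration of the data collected, we decided to change the SAP". It adds: "Estimated t-values, 95% confidence intervals, and p-values will be presented for each outcome variable". Section 5 describes the study plainly: "This pilot study is a non-controlled clinical trial consisting of one group of participants". Section 7 says the tests serve "to describe changes in primary and secondary outcomes from baseline to 14 days post infusion". The Introduction and Aims still ask whether such a study is acceptable and feasible in youth.

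**Protocol.** The post-infusion monitoring section and the instrument description both name CY-BOCS as the primary measure. The independent evaluator's schedule includes baseline, day 7 and day 14.

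**The concern.** A test and comparison settled with the data in hand give an exploratory p-value, whatever its size. A reader who meets it under a primary heading will take it as prespecified unless told otherwise. The sentence in section 8.2 gives the timing, but nothing in section 6.1 or in the reporting rule changes the rank of the result.

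The second half concerns the pilot's first question. If the plan no longer calls for the numbers screened and completing, a report that follows it faithfully could answer the efficacy question and not the feasibility one. Both SAP versions say promising data will support a grant application for a full-scale randomized trial. Recruitment and completion figures are what that trial would be planned on.

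**Working it through.** The documents give no effect size, standard deviation, power or alpha for these tests, so there is no planned figure to reproduce. The check sets the texts side by side.

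| Item | Protocol | Initial SAP | Revised SAP |
|---|---|---|---|
| Numbers screened and completing | Not named as outcomes; Aim 1 covers acceptability, feasibility, tolerability | Primary | Not listed |
| CY-BOCS | Primary measure; day 7 and day 14 | Secondary; weeks 1 and 2 | Primary; day 14 only |
| CGI-S | CGI collected, not ranked | Not mentioned | Primary; day 14 |
| OCD-VAS | Collected | Not in outcome list, but change in obsessional severity to post-infusion is in the model (8.2) and Procedures measures it by OCD-VAS | Secondary; day 14 |
| Y-BOCCS | Collected | Not mentioned | Secondary; day 14 |
| CDRS-R | Collected | Secondary; weeks 1 and 2 | Not listed |
| Response and low final score | Decrease ≥30%; score ≤10 | Decrease ≥35%; score ≤12 | Not listed |
| Adverse events, C-SSRS | Collected | Listed (6.3) | Listed (6.3) |
| Test | None named | Mixed-effects regression | Paired t-test |

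**Step 1: what is stated to be post-data.** The dated sentence in section 8.2 covers the move to paired t-tests and the baseline-to-day-14 comparison. It does not cover the outcome list. When CGI-S became co-primary, and when the counts were removed, is not stated.

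**Step 2: what is new.** CY-BOCS as the efficacy measure is not new to the trial, because the protocol names it. CGI-S as co-primary is new. So is day 14 as the only tested time point: Procedures in the revised SAP still describes weekly CY-BOCS ratings for two weeks, so week-1 data are scheduled but no longer tested.

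**Step 3: is the status labelled?** In the revised text from the Introduction to the References, neither a post hoc nor an exploratory label appears. The front matter of the revised version was not in the text available, so a label there cannot be excluded.

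**Step 4: is Aim 1 still measured?** Sections 6.1 and 6.2 contain four rating-scale changes. Section 8.1 calls all primary and secondary outcomes continuous, which leaves no place for counts. Section 6.3 keeps adverse events and C-SSRS, which bear on tolerability and safety. Nothing measures recruitment or completion, and the available text gives no reason for the removal.

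**Step 5: size.** The bias depends on which alternatives were looked at and what they showed, and the documents say neither. For scale only, suppose two-sided alpha 0.05 and that the smaller p-value of two null paired t-tests were reported. If the tests are independent, the error rate is 1 − 0.95² = 0.0975. Simulation (200,000 replicates) gives about 0.098 at zero correlation, and 0.083 (n = 5) or 0.081 (n = 10) at correlation 0.8. This describes a search that the documents do not report; it is not an estimate for this trial.

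**The case against.** The strongest reply is that the revised SAP already discloses the point. In the section that defines the tests, it says the method was changed and that this followed the data. It calls the study a non-controlled pilot and uses the tests to describe changes. On this view the missing word is a matter of style. The part that stands is that there is no concealment. However, a pilot design and a descriptive purpose do not tell the reader that the comparison was chosen with the data in hand, and the primary rank with p-values points the other way.

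A second reply is that ranking CY-BOCS first brings the SAP towards the protocol, which never made the counts primary. That is correct for CY-BOCS. It does not supply a measure for Aim 1, which both documents retain. The protocol places C-SSRS under a feasibility and safety heading and says the 3-month visit helps to evaluate satisfaction. These touch on acceptability but do not show how many young people were screened or finished.

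A reader might also infer more than the documents support:

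- **That day 14 was chosen because it looked favourable.** No results are given, and no motive is stated.
- **That the primary outcomes were swapped after the data were seen.** The post-data statement covers the test and the day-14 comparison only.
- **That the initial plan was abandoned wholesale.** Adverse events and C-SSRS are kept, and a change in obsessional severity, measured by OCD-VAS, was already planned; its day-14 timing is what is new.
- **That the counts will not be reported.** The revised SAP no longer calls for them, but does not bar them.

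**Conclusion.** The point holds in two parts. First, the day-14 paired t-tests are post-data choices by the SAP's own statement, yet two are ranked primary and all carry p-values with no exploratory label in the available text. The defect is the status given to the results. Second, the acceptability and feasibility aim has no recruitment or completion outcome in the revised version.

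The bias from the post-data choice cannot be quantified from the documents. The conclusion rests on the wording of sections 6.1, 6.2, 8.1 and 8.2 of the revised SAP, and on the assumption that the unavailable front matter contains no label. It matters because it determines what the pilot can claim: an exploratory efficacy signal, and a feasibility answer only if the counts are reported.

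**What to change.** 1. In revised sections 6.1 and 8.2, label the day-14 paired t-tests post hoc or exploratory. Report estimates with 95% confidence intervals and treat p-values as descriptive. Say that the protocol named CY-BOCS in advance and that CGI-S was added as a primary outcome in the revision.
2. In 6.1, restore number screened and number completing as the Aim 1 outcomes. Define completing and the denominator, and report totals and percentages; an exact confidence interval is optional. Amend 8.1 to allow counts.
3. Report the week-1 CY-BOCS change, and the CDRS-R and responder and remitter results planned in the initial SAP. The cut-offs conflict (≥35% and ≤12 in the initial SAP; ≥30% and ≤10 in the protocol), so report both sets; picking one now would be another post-data choice.
4. For each changed outcome or time point, state whether the change came before or after data review.

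The cost is SAP wording and a few tables from data the protocol already schedules. No study procedure changes. The price is a more modest, exploratory efficacy claim.
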